## 4 ANALYSIS DETAILS

### 4.1 ENROLMENT AND ELIGIBILITY

The following results will be presented overall, and by stratum:

- Total screened for enrolment and enrolled by site, with dates of first and latest enrolment
- Reasons for not enrolling screened patients
- Enrolment over calendar time: cumulative enrolment; enrolment by calendar month
- Eligibility: number (%) and reasons for any ineligibilities (i.e. enrolled although eligibility criteria violated)

### 4.2 RANDOMISATION AND ELIGIBILITY

The following results will be presented overall, by stratum, and by randomised group:

- Total screened for randomisation by site
- Total randomised by site, with dates of first and latest randomisation
- Reasons for not randomising screened patients
- Randomisation over calendar time: cumulative randomisation; randomisation by calendar month
- Eligibility: number (%) and reasons for any ineligibilities

### 4.3 PATIENT CHARACTERISTICS

The following baseline characteristics will be presented overall and by randomised group. For the grouping of quantitative variables, categories will be chosen after univariate inspection of the data, ensuring that a reasonable number of participants are represented in each category.

Before completion of randomisation, the same characteristics will also be reported for all patients enrolled but not by randomised group.

- Stratum: number (%) stratum I, stratum II
- Age: median (IQR), range; distribution in categories
- Sex: number (%) male, female
- Ethnicity: number (%) White, South Asian, South East Asian, Hispanic/Latino, Black African, Black Caribbean/American, mixed ethnic group, other
- Mode of HIV infection: number (%) sex between men, sex between men and women, injection drug use, blood products, unknown, other
- CD4 count (current): median (IQR), range; distribution into categories
- HIV-RNA: number (%) undetectable; distribution into categories
- Criteria for PHI diagnosis: number (%) positive HIV-1 serology, positive p24, HIV RNA or proviral DNA, 4th generation HIV test, western blot, RITA only.
- eGFR: median (IQR), range
- QTc interval: median (IQR), range
- Haematology/biochemistry/electrolytes/glucose/lipids/urine analysis: median (IQR), range of test results

#### 4.4 DESCRIPTION OF FOLLOW-UP

- Time between randomisation and last follow-up (weeks): median (IQR), range
- Attendance of scheduled visits, by visit: number (%) missed visits. Denominator to include any patients withdrawn or lost to follow-up, but not any known to have died.
- Additional visits compared with schedule: number (%). Denominator to include visits for any patients withdrawn or lost to follow-up, but not any known to have died.
- Early end of trial participation: number (%); description of reasons.
- End of treatment without end of trial participation: number (%).

For reports while the trial is ongoing:

- Time between enrolment and randomisation (weeks) in stratum I: median (IQR), range
- Lost to follow-up: number (%) formally defined as lost to follow-up (not seen in the clinic for more than 3 months), subdivided by formal ending of trial participation (yes/no)
- Transfer to a new site: number (%)
- Last attended scheduled visit: number (%)

#### 4.5 DESCRIPTION OF TRIAL TREATMENT

**ART pre-randomisation:**

- First regimen: number (%) per regimen
- Time from PHI diagnosis to starting ART: median (IQR), range; distribution into categories  $\leq 1$  week, 1-2 weeks, 3-4 weeks.
- ART pre-PHI diagnosis: number (%) pre-exposure prophylaxis, post-exposure prophylaxis
- Time from starting ART to randomisation: median (IQR), range; distribution into categories  $\leq 24$  weeks, 24-48 weeks, 48-96 weeks,  $>96$  weeks.

**ART from randomisation:**

- ART regimen at randomisation: number (%) 3-drug/4-drug regimen, number (%) on integrase inhibitor, number (%) per regimen
- ART changes: number (%) making changes, reasons for changes, drugs changed to; time to first change
- ART discontinuation: number (%) with permanent discontinuation of all ART ( $>30$  days), description of reasons
- Regimen at last follow-up: number (%)
- Drug class exposure: number (%) ever exposed to 2, 3, 4 classes of drugs (i.e. cumulative to date)
- Non-adherence: any dose of ART missed since last visit: number (%); any dose missed in last 7 days: number (%), overall and by drug; how many doses of ART missed in last 7 days: number.

**Vaccines (participants randomised to arm B only):**

- Not received ChAd vaccination: number (%); description of reasons
- Not received MVA vaccination: number (%), description of reasons

**Vorinostat (participants randomised to arm B only):**

- Not started vorinostat: number (%); description of reasons
- Treatment deviations/modifications: number (%) with dose modification, missed doses, treatment discontinuation; description of reasons

## 4.6 PRIMARY ENDPOINT

The primary outcome measure is based on total HIV DNA from CD4 T-cells (copies/million CD4+T cells) which is measured at enrolment (in recently infected patients), baseline, PR week 08-3, PR week 12-2, PR week 16, and PR week 18.

The primary endpoint is total HIV DNA averaged across post-randomisation weeks 16 and 18. It will be analysed on a  $\log_{10}$ -scale. Treatment arms will be compared in terms of absolute total HIV DNA levels at post-randomisation weeks 16 and 18 adjusted for the baseline (i.e. randomisation) level and by stratum using analysis of covariance.

Each sample of a particular time-point is measured in triplicates. Any result below the lower detection limit (LDL) - including undetectable DNA but NOT missing values - will be replaced by LDL/2. A value of 5 HIV copies/well will be adopted as lower limit of detection.

### **Handling of missing total HIV DNA measurements**

If either the PR week 16 result or the PR week 18 result is entirely missing but not both, the primary endpoint consists of the single available result. If total HIV DNA is missing at both PR-16 or PR-18, or at baseline, an imputation method will be used to estimate missing values. Predictors may include stratum, total HIV DNA from previous time-points and other factors associated with total HIV DNA eg CD4.

### **Sensitivity analyses for the primary endpoint**

The following sensitivity analyses for the primary endpoint will be performed:

- With the per protocol population, i.e. excluding participants with incomplete intervention (temporary/complete stop of ART, vaccination, or vorinostat).
- Complete case analysis: excluding participants with missing primary endpoint

## 4.7 SECONDARY ENDPOINTS: EFFICACY

- HIV integrated DNA:**

Measurements (copies/million CD4+T cells) at enrolment (in recently infected patients), baseline, PR week 08-3, PR week 12-2, PR week 16, and PR week 18.

Analysed as for continuous outcomes as specified above. Treatment arms will be compared in terms of absolute integrated HIV DNA levels at post-randomisation weeks 16 and 18 adjusted for the baseline level and by stratum.

- Plasma HIV RNA measured with an ultra-low copy assay:**

Number (%) with undetectable HIV-RNA at enrolment (in recently infected patients), baseline, PR week 08-3, PR week 09-2, PR week 12-2, PR week 16, and PR week 18; analysed as for binary outcomes as specified above.

- **Replication competence (Viral Outgrowth assay):**

Measurements (infectious units per million cells; IUPM) at baseline and PR week 16. Analysed as for binary and continuous outcomes as specified above. The results are expected to be “negative” (i.e. below the lower limit of detection) in a sizable proportion of samples. Therefore, the treatment arms will be compared as follows:

- 1) Primary analysis:
  - a) Comparison of the proportion of patients with a “negative” result using logistic regression. This analysis includes all patients with a valid PR-16 result.
  - b) Comparison of IUPM in patients with “positive” results using median regression. Patients with a “negative” PR-16 result will be excluded.
- 2) Secondary analysis:  
Comparison of IUPM using a linear model appropriate for left-censored data. This analysis includes all patients with a valid PR-16 result, “positive” or “negative”.

In all analyses, patients with missing PR-16 samples or invalid PR-16 results (due to assay failure) will be ignored. Analyses will be adjusted for stratum and baseline viral outgrowth. Missing baseline values will be imputed; predictors may include stratum, and other factors associated eg CD4, HIV-DNA.

- **HIV-specific T cell responses (both CD8+ and CD4+ T cell responses):**

Measurements using intracellular cytokine staining (ICS) at enrolment (in recently infected patients), baseline, PR week 09-2, PR week 12-2, and PR week 16. For both CD8+ and CD4+ T cells, the following markers will be measured: CD107a+, CD154+, IFNg+, IL2+, and TNFa+.

For each marker, the magnitude of a response is defined as the number of positive cells as percentage of their parental populations, after subtracting the negative control. For technical reasons, HIV antigens will be divided in non-overlapping pools values for each sample; responses will be added up for each marker.

At each time-point, the magnitude of responses, and the change from baseline will be analysed as for continuous outcomes as specified above.

- **CD8+ T cell antiviral activity (viral inhibition)**

Measurements using a flow cytometer-based assay [2] at enrolment (in recently infected patients), baseline, PR week 09-2, PR week 12-2, and PR week 16.

CD8+ T cell antiviral suppressive activity will be expressed as percentage inhibition and determined as follows:  $\frac{[(\text{fraction of p24} + \text{cells in CD4} + \text{T cells cultured alone}) - (\text{fraction of p24} + \text{in CD4+ T cells cultured with CD8+ cells})]}{(\text{fraction of p24} + \text{cells in CD4} + \text{T cells cultured alone})} \times 100$ .

CD8+ T cell antiviral suppressive activity will be analysed as described above for continuous outcomes.

- **Inflammatory biomarkers:**

For example CD4:8 ratio, immune exhaustion/activation markers, IL-6 and d-dimer, neuro-inflammation markers. Analysed as for continuous outcomes as specified above.

- **HIV cell associated RNA (arm B only):**

Measurements (copies/million 18S copies) pre and 2 hours post vorinostat at visits PR week 08-3, PR week 09-2, and PR week 12-2. Comparison of pre and post vorinostat values will be performed using paired t-tests (or paired rank-tests if appropriate).

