## 1.4 SAMPLE SIZE

The sample size calculation is based on the primary endpoint which will be analysed on a  $\log_{10}$ -scale. The following assumptions are made:

- The combination intervention will confer a 50% reduction in total HIV DNA when compared with cART alone. On a  $\log_{10}$ -scale this corresponds to a difference between the two arms of  $\log_{10}(2)$  (approximately 0.3). The effect is assumed to be the same in both strata (recently and previously diagnosed patients).
- Standard deviation (SD) is 0.4 for a single measurement in both arms based on two publications:
  - Reported on data from 31 participants treated with HAART at PHI in the French PRIMO study. The median (IQR) at 6 and 12 months after starting treatment were 2.30 (2.10, 2.70) and 2.10 (1.80, 2.40)  $\log_{10}$  DNA copies/ $10^6$  PBMC respectively suggesting a SD of 0.45 at both time points.
  - Reported on 8 participants with PHI. At week 52, the median (IQR) was 494 (250 - 694) for total HIV-1 DNA copies/ $10^6$  CD4+ T-cells suggesting a SD (in log scale) of 0.33.
- 1:1 allocation of participants in the two study arms.
- Method of analysis: comparing the treatment arms in terms of absolute HIV total DNA level at post-randomisation weeks 16 and 18 adjusted for baseline (here: randomisation) level (analysis of covariance; ANCOVA); one baseline measurement and two follow-up measurements (at PR16 and 18) will be taken for an individual participant.
- A correlation coefficient of 0.5 between a baseline measurement and a PR 16/18 measurement, and a correlation coefficient of 0.7 for measurements at PR 16 and 18.
- Two-sided  $\alpha = 0.05$  for the null hypothesis that there is no difference between the two arms in the primary endpoint.

Under the above assumptions, a sample size of 52 individuals would provide 94% power to detect a 50% reduction in HIV total DNA (86% power for a 45% reduction).

Assuming that some individuals enrolled will not reach visits PR 16/18 (due to failing the eligibility criteria for randomisation in stratum I, or withdrawal) it is planned to enrol a total of 60 individuals overall (both strata combined).

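### Viral outgrowth part 1(b) compares IUPM only among participants positive at PR-16, so it is not a randomised comparison and would understate a uniform fall in IUPM

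*SAP*

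**What the plan says.** SAP section 4.7 (Replication competence) measures IUPM at baseline and PR-16 and expects results below the detection limit "in a sizable proportion of samples". It plans three analyses:

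- Primary, part 1(a): "Comparison of the proportion of patients with a “negative” result using logistic regression. This analysis includes all patients with a valid PR-16 result".
- Primary, part 1(b): "Comparison of IUPM in patients with “positive” results using median regression. Patients with a “negative” PR-16 result will be excluded".
- Secondary: "Comparison of IUPM using a linear model appropriate for left-censored data. This analysis includes all patients with a valid PR-16 result", whether positive or negative.

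Two rules cover all three. On covariates: "Analyses will be adjusted for stratum and baseline viral outgrowth". On failed assays: "In all analyses, patients with missing PR-16 samples or invalid PR-16 results (due to assay failure) will be ignored".

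SAP section 3 makes intention-to-treat the main principle and log-transforms positively skewed continuous data. Section 4.7 does not point out that 1(b) conditions on a post-randomisation result, and does not say how the three results are to be read together.

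**The concern.** The intervention is meant to shrink the reservoir, so whether a participant is still positive at PR-16 is itself an outcome. If arm B lowers IUPM by a similar factor in everyone, its low-IUPM participants fall below the limit and leave 1(b), while their counterparts in arm A stay in. The remaining arm B participants are those who started higher, and the difference between arms shrinks.

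Part 1(a) gives no size of effect on IUPM. Part 1(b) therefore supplies the only IUPM effect size that is ranked primary for this endpoint. Without a label, its smaller difference could be reported as the effect of the intervention on IUPM. The analysis that does estimate that effect in all valid results is ranked second.

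**Working it through.** **1. The plan's own figure.** The documents state no figure for viral outgrowth. The nearest is the power for total HIV DNA in SAP section 1.4. Residual SD = 0.4 × √[(1 + 0.7)/2 − 0.5²] = 0.310. With 26 per arm, SE = 0.310 × √(2/26) = 0.0859. Power for a halving = Φ(0.301/0.0859 − 1.96) = 93.9%; for a 45% fall, Φ(0.260/0.0859 − 1.96) = 85.6%. These match the stated 94% and 86%, and the point below does not touch them.

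**2. Inputs for IUPM.** All are assumptions. The halving is borrowed from a statement about another measure ("The combination intervention will confer a 50% reduction in total HIV DNA when compared with cART alone"), as is the lowest correlation ("A correlation coefficient of 0.5 between a baseline measurement and a PR 16/18 measurement"). Assumed: log10 IUPM normal, SD 0.4-0.7, 20-60% of controls negative, the same shift of −log10(2) = −0.301 for everyone in arm B, and correlation 0.5-0.9 between baseline and PR-16. No stratum effect was included.

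**3. Unadjusted, closed form.** For mean m, SD s and limit l, the median above the limit is m + s × Φ⁻¹{[1 + Φ((l − m)/s)]/2}. Take s = 0.4 and half of controls negative (l = 0, control mean 0).

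- Arm A: 0.4 × Φ⁻¹(0.75) = 0.270.
- Arm B: Φ(0.301/0.4) = 0.774, so 77% are negative; −0.301 + 0.4 × Φ⁻¹(0.887) = 0.183.
- Apparent reduction: 1 − 10^(0.183 − 0.270) = 18%, against a true 50%.

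Over the whole grid the apparent reduction is 15-32%, with 34-84% of arm B negative.

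**4. Adjusted for baseline, as the SAP requires.** Large-sample simulation of median regression among positives on arm and baseline, with baseline either fully observed or set to half the limit when negative:

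| True uniform fall | Correlation 0.5 | 0.7 | 0.9 |
|---|---|---|---|
| 50% | 17-35% | 22-38% | 35-46% |
| 30% | 11-21% | not run | 19-28% |
| 70% | 26-49% | not run | 50-64% |

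For the true halving, the left-censored model on all participants gave 47-51%.

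**5. Why adjustment is only partial.** With 40% of controls negative, positives in arm B had a baseline 0.09-0.10 log10 higher than positives in arm A at correlation 0.5, and 0.17-0.18 higher at 0.9. Conditioning on baseline leaves selection on the rest of the PR-16 value.

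**6. How far the ranges move.**

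- Share negative: with 10-70% of controls negative and SD up to 1.0, 15-41% at correlation 0.5 and 31-48% at 0.9.
- Scale: on raw IUPM, 16-31% at 0.5 and 13-34% at 0.9.
- True zeros: if 15-40% of both arms have no inducible virus (30-60% of controls negative in total), 1(b) shows 19-43% and the censored model 44-49% at 0.5; 37-49% and 46-51% at 0.9.
- No effect: both arms are cut at the same limit from the same distribution, so 1(b) is not biased.
- Selective clearance: if only the lowest 20-40% of arm B positives turn negative and nobody else changes, the adjusted arm B median among positives is 15-92% higher at 0.5 and 6-29% higher at 0.9, while 1(a) points to benefit.

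**The case against.** The SAP foresees many negatives and plans a package for them. Two of its three analyses keep every valid result, and the remedy is largely in the plan already. Asking whether virus grows and, if so, how much is a recognised two-part description; the text of 1(b) says openly that it concerns positives and never claims to estimate the effect in everyone. The percentages rest wholly on assumptions. At trial size noise is larger than the distortion: in simulated trials of 52 with a true halving (correlation 0.5, SD 0.7, 40% of controls negative), the 5th to 95th percentile of 1(b) ran from a 63% reduction to a 75% increase. The censored model has weaknesses too. Under selective clearance it gave a 7-53% reduction, a uniform ratio that describes nobody.

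Most of this stands, and it limits the point to the rank and reading of 1(b). It does not make 1(b) a randomised comparison: noise comes on top of the attenuation and does not cancel it. On precision at 52 participants, one set of runs found the censored model worse at SD 0.4 with 60% of controls negative (RMSE 0.35 against 0.26 log10 at correlation 0.5), although 1(b) could not be fitted in about 20% of those runs. A further check did not reproduce this among runs where 1(b) could be fitted, and in four settings the censored model did better (0.11-0.19 against 0.18-0.27).

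A reader might infer that the whole viral outgrowth analysis is invalid, or that 1(b) would create an effect where there is none. The documents support neither: 1(a) and the censored model keep all valid results by arm, and with no effect both arms are selected alike.

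**Conclusion.** The concern holds for part 1(b) alone. It compares groups defined by a post-randomisation result that treatment can change, so it does not estimate the effect on IUPM in all participants, and the required baseline adjustment corrects this only in part. A uniform fall is attenuated; other patterns can distort 1(b) differently.

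The 17-35% and 35-46% for a true halving are illustrations. They depend on log-normal IUPM, the log scale, a uniform effect, SD 0.4-0.7 log10 and 20-60% of controls negative, none of which the documents state for IUPM. They should not be read as a forecast for this trial. It might also be inferred that the main result or the trial's power is at risk; total HIV DNA is analysed separately and neither is affected. This is a cheap improvement of minor severity on a secondary endpoint.

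**What to change.** Amend SAP section 4.7 as follows:

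- Keep 1(a) as the primary analysis.
- Report 1(b) as descriptive medians among positives by arm, labelled as conditional on a post-randomisation result, with no between-arm test.
- Take the IUPM effect estimate from the planned left-censored model on all valid PR-16 results, adjusted for stratum and baseline.
- Add one sentence on how the results are read together.
- Optional check: a stratified rank comparison of all valid results with negatives tied lowest. It needs no distributional assumption, but gives no IUPM ratio and is not baseline-adjusted.

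The cost is SAP wording only, with no new samples or assays. The downside is that the censored model relies on an assumed distribution below the detection limit, which matters more when many results are negative or some participants have no inducible virus. It also describes selective clearance of low-level virus less well than 1(a) with the descriptive 1(b), which is why both stay in the report.

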#### 4.8 SECONDARY ENDPOINTS: SAFETY

Adverse events pre-randomisation will be presented overall. Adverse events post-randomisation will be presented by randomised arm. For all adverse event types, the total number of events, the number of participants with at least one event, and the maximum grade per participant will be given. Analysis of adverse event outcomes will be based on the number ever experienced a type of adverse event which will be compared as for binary outcomes. Timing of events, and recurrent events will also be described.

Where relevant and established, events will also be presented by severity grade, and by relationship to study treatment (definitely, probable, possible, unlikely, unrelated).

The following adverse event outcomes will be analysed:

- Grade 3 or 4 adverse events
- Notable events
- Treatment-modifying adverse events (any grade)
- Post-vaccination solicited events (arm B only; any grade):
  - solicited local injection site reactions: pain, itching, redness/blistering
  - solicited general reactions: fever, muscle aches, generalised itching, joint aches, headache, nausea, general discomfort
- SAEs, overall and by type of SAE (fatal, life-threatening, hospitalisation, disability, other).
- Lab abnormalities.
- Tabulation of adverse events of all grades

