#### 1.1.1.C CLINICAL EXPERIENCE WITH HDACi IN OTHER DISEASE AREAS

HDACi have shown efficacy in relapsed/refractory myelodysplasia (MDS), acute myeloid leukaemia Hodgkin lymphoma (HL) and in particular the T cell lymphomas. In the US vorinostat is licensed (since 2006) for the treatment of cutaneous manifestation of CTCL in those who have progressive, persistent or recurrent disease on or following two systemic therapies. It has also been granted orphan drug status for the treatment of refractory multiple myeloma in the US (October 2013). In the EMEA, vorinostat was granted orphan designation for use in malignant mesothelioma in September 2010; but this was withdrawn at the Sponsor (MSD) in February 2013. Other HDACi such as romidepsin (depsipeptide), panobinostat and MGCD-0103 have also demonstrated activity in various haematological malignancies. Further information on the toxicity profile of vorinostat is provided in [Appendix II](#) but in summary – in the cancer setting, the most common drug-related adverse reactions can be classified into four symptom complexes.

1. Gastrointestinal symptoms - Anorexia, nausea, vomiting, diarrhoea, weight loss and constipation.

2. Constitutional symptoms - Fatigue has been reported commonly with use of vorinostat and occurred more commonly at doses of vorinostat >400mg per day. Chills and fever have also been reported.
3. Abnormalities - Dose-related anaemia and thrombocytopenia can occur with vorinostat and are more common at doses of >400mg per day. Neutropenia is uncommon, but has been reported. Monitoring of blood cell counts should be performed every 2 weeks during the first 2 months of therapy and monthly thereafter. If platelet counts and/or haemoglobin are reduced during treatment with vorinostat, the dose should be modified or therapy discontinued.
4. Taste disorders - Dysgeusia and dry mouth have been reported.

The most common serious adverse events (SAE), regardless of causality, in the 86 CTCL patients in two clinical studies were pulmonary embolism reported in 4.7% (4/86) of patients, squamous cell carcinoma reported in 3.5% (3/86) of patients and anaemia reported in 2.3% (2/86) of patients. Patients on vorinostat should therefore be monitored for pertinent signs or symptoms of deep vein thrombosis or pulmonary embolism.

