## 5.4 POST-RANDOMISATION (PR) TREATMENT

Once a participant has been randomised to the study the participant allocation will be confirmed by the RIVER Co-ordinating Centre. Participants in Arm B will be scheduled for their first vaccination at Royal Free Hospital as per treatment schedule see [Figure 5](#).

ARM	COMPONENT	DETAIL
Arm A: cART preferably including raltegravir	Combination ART (cART)	Likely consisting of an Nucleoside reverse-transcriptase inhibitor (NRTI) backbone i.e. Truvada® and raltegravir. cART is prescribed at enrolment/randomisation for the duration of the study Raltegravir dosage: oral 400mg tablet twice per day (BID). SmPC: Current version as posted to www.medicines.org.uk Marketing Authorisation Holder: Merck Sharp & Dohme Ltd
	Combination ART (cART)	Likely consisting of an Nucleoside reverse-transcriptase inhibitor (NRTI) backbone i.e. Truvada® and raltegravir. cART is prescribed at enrolment/randomisation for the duration of the study Raltegravir dosage: oral 400mg tablet twice per day (BID). SmPC: Current version as posted to www.medicines.org.uk Marketing Authorisation Holder: Merck Sharp & Dohme Ltd
	ChAdV63.HIVconsv (ChAd)	Dosage: $5 \times 10^{10}$ vp Administration: This dose is obtained by injecting 0.37ml of the vaccine at $1.35 \times 10^{11}$ vp/ml without dilution. This prime vaccination is administered intramuscularly (IM) into the deltoid muscle of the non-dominant arm within 1 week of randomisation at visit post-randomisation week 00 (PR00). Manufacturer: Clinical BioManufacturing Facility (CBF), Oxford, UK Storage: Vials are stored at between -70 and -90°C
	MVA.HIVconsv (MVA)	Dosage: $2 \times 10^8$ pfu Administration: This dose is obtained by injecting 0.23 ml of the vaccine IM at $8.6 \times 10^8$ pfu/ml without dilution. This boost vaccination is administered intramuscularly (IM) into the deltoid muscle of the non-dominant arm at post-randomisation week 8 Day 1 (PR08-1), 2 days prior to start of vorinostat. Manufacturer: Impfstoffwerk Dessau-Tornau (IDT) Biologika GmbH, Germany Storage: Vials are stored at between -70 and -90°C

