### 5.6.3 VACCINES

Irrespective of clinical site of enrolment, all vaccine study visits for the Arm B participants will be undertaken at one centralised vaccine site (Royal Free Hospital). The reason for this is to ensure uniform temperature and GMP procedures for vaccine procurement, storage, thawing and administration.

The first vaccination (ChAd) takes place at post-randomisation week 00 (PR00), within 1 week after randomisation, and the second vaccine (MVA), 8 weeks later, at PR week 08 day 1 (PR08-1). There is a visit window around the second vaccine of 7 days. On the days of vaccination, the vaccine will be allowed to thaw to room temperature and then administered within 1 hour of removal from the freezer. The vaccine will be administered intramuscularly (IM) over the deltoid region of the non-dominant arm. The investigator or study nurse will wear gloves and eye protection. During administration of the vaccines, medicines and resuscitation equipment will be immediately available for the management of anaphylaxis. The participant will remain in clinic for  $\geq 1$  hour of observation following the receipt of each vaccine. The participant will be contacted by phone by designated study personnel within 72 hrs of receipt of both vaccines to review any AEs. Participants should complete a 3 day vaccine diary following each vaccination.

In order to minimise dissemination of the recombinant vectored vaccine virus into the environment, the inoculation sites will be covered with a dressing after immunisation. This should absorb any virus that may leak out through the needle tracks. The dressings will be removed from the injection sites after 30 minutes and disposed of as genetically modified organism (GMO) waste by autoclave and then standard disposal, in accordance with current standard UK practice.

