### 5.6.4 VORINOSTAT

Procedures for proper handling and disposal of vorinostat as cytotoxic drug should be employed. The drug should only be dispensed at Royal Free Hospital to those randomised to Arm B. Total number of doses is 10 x 400mg doses over 28 days with 4 x 100mg capsules taken every third day with food. Vorinostat will be dispensed to participants on PR week 08 day 1 (PR08-1) at the Royal Free Hospital at the participant's second vaccination visit. Participants will be required to bring their vorinostat to their clinic visit (at recruiting site) at PR week 08 day 3 (PR08-3). Participants will be required to take their first vorinostat dose in clinic. Ideally, Day 1 of vorinostat dosing will occur on a Wednesday to avoid study blood draws over the weekend. Dosing should be undertaken at the same time each day. Vorinostat must be kept at room temperature, 15°-30°C (59°-86°F). Vorinostat capsules if damaged or broken should not be used. Vorinostat capsules must not be opened or crushed. If vorinostat powder (within the capsule) comes into contact with skin or mucous membranes, the area must be washed immediately with plain water; participants should notify the site.

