### 2.3 ADVERSE EVENTS

Adverse events will be reported on the case report form. Prior to randomisation only grade 3 and 4 adverse events and Serious Adverse Events (SAE) are collected. Post-randomisation, all adverse events will be reported including grade 1 and 2 events, and other notable events (see below).

All clinical events reported during the trial will be reviewed by the Trial Physician (unblinded). Adverse events will be classified by system organ class and lower level term according to the version of MedDRA® implemented at the start of the trial (version 19; the same version will be used throughout).

Adverse events (clinical and laboratory) will be graded using the 2004 (amended 2009) Division of AIDS toxicity grading table (see Appendix III of RIVER protocol).

Serious adverse events will be defined according to principles of GCP.

Other notable events, to be reported on designated CRFs: Vaccine-related events (see Appendix IV of the RIVER protocol), Cancer, Pregnancy in a partner.

Solicited adverse events following the receipt of each vaccine will be recorded on a CRF during the first 60 mins by clinical staff, and then daily by the participant on a diary card for 3 days.

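### The three-day diary after the MVA boost runs past the first vorinostat dose, so nausea or fever that begins after that dose can be counted as a post-vaccination event

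*SAP*

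**What the plan says.** Protocol 5.4 places the MVA boost "at post-randomisation week 8 Day 1 (PR08-1), 2 days prior to start of vorinostat". Protocol 5.6.4 adds, for the PR08-3 visit: "Participants will be required to take their first vorinostat dose in clinic". The whole course is described there as follows: "Total number of doses is 10 x 400mg doses over 28 days".

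On collection, Protocol 5.6.3 says: "Participants should complete a 3 day vaccine diary following each vaccination". SAP 2.3 has staff record solicited events for the first 60 minutes, "and then daily by the participant on a diary card for 3 days".

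On analysis, SAP 4.8 lists "Post-vaccination solicited events (arm B only; any grade"), divided into local injection-site reactions and "solicited general reactions: fever, muscle aches, generalised itching, joint aches, headache, nausea, general discomfort". Adverse event outcomes are analysed by whether a participant ever had an event of that type, and the maximum grade per participant is also given. SAP 4.8 does not say that ChAd and MVA are tabulated separately, and it does not divide the post-MVA diary at the first vorinostat dose.

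Protocol 1.1.1.C lists among the common drug-related reactions to vorinostat "Gastrointestinal symptoms - Anorexia, nausea, vomiting, diarrhoea, weight loss and constipation". Under constitutional symptoms it also mentions fever.

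**The concern.** A diary meant to capture what follows a vaccine is, after the boost, still open when a second investigational product is started. Two of the seven solicited general terms, nausea and fever, are reactions that the protocol itself ascribes to vorinostat. A same-day effect is plausible, since Protocol 1.1.1.A gives a median of 4 hours to maximum concentration when vorinostat is taken with food.

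With ever/never counting, a single entry after the dose can turn a participant into a case, and it can also raise that participant's maximum grade. The contamination can only add to the count. The ChAd diary has no such overlap, so the two post-vaccination windows in arm B are not alike. If the SAP table pools the two vaccines, the overlap cannot be seen at all.

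**Working it through.** **Schedule.** Count PR08-1 as day 1. The first vorinostat dose, at PR08-3, is day 3. The last dose, at PR12-2, is day 4 × 7 + 2 = 30. Dosing every third day gives (30 − 3)/3 + 1 = 10 doses over 30 − 3 + 1 = 28 days. Both figures agree with Protocol 5.6.4. The gap from MVA to vorinostat is 3 − 1 = 2 days, as Protocol 5.4 states.

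**Overlap of the diary with vorinostat.** The documents do not say whether diary day 1 is the day of vaccination or the day after, so both are shown.

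| Reading | Diary days | On or after first dose | Vorinostat-free days |
|---|---|---|---|
| Day 1 = day of vaccination | 1, 2, 3 | 1 of 3 (day 3) | 2 |
| Day 1 = day after vaccination | 2, 3, 4 | 2 of 3 (days 3 and 4) | 1 |

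ChAd is given at PR00, about 8 weeks before MVA, so 0 of 3 ChAd diary days overlap.

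**What could separate the two products.** SAP 4.8 promises a general description of the timing of events, but names no split at the vorinostat dose. It presents relationship only where relevant and established, and to study treatment as a whole. Protocol 7.4.1.C requires a causality assessment for serious events only. Nothing therefore obliges anyone to attribute a non-serious diary entry to MVA or to vorinostat.

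**Size, by illustration only.** The documents give no daily event rates. Let p be the proportion with a solicited general reaction from MVA alone, and q the proportion with one caused by vorinostat in the overlap. Both are assumed, and taken as independent. The tabulated proportion is 1 − (1 − p)(1 − q), so the increase is q(1 − p). Arm B is taken as 60/2 = 30, which supposes that everyone enrolled is randomised.

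| p | q = 5% | q = 10% | q = 20% |
|---|---|---|---|
| 10% | +4.5 points (1.4 of 30) | +9 (2.7) | +18 (5.4) |
| 30% | +3.5 (1.1) | +7 (2.1) | +14 (4.2) |
| 50% | +2.5 (0.8) | +5 (1.5) | +10 (3.0) |

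The increase is always less than q itself, because a participant who has already reacted to MVA cannot be counted a second time. At q = 10%, the 3 participants obtained from 10% × 30 are a ceiling, reached only if none of them had reacted earlier in the diary.

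**The case against.** The strongest reply is that the SAP label describes a time window and not a cause. A reader might infer that the plan attributes vorinostat reactions to MVA, but SAP 4.8 specifies no MVA reactogenicity rate and no comparison of ChAd with MVA. That reply stands: such events can be counted as post-vaccination, and the plan does not call them MVA reactions.

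A reader might also infer that an early vorinostat effect would be hidden. The documents do not support this. After randomisation adverse events of every grade are reported (Protocol 7.4, SAP 2.3), and SAP 4.8 tabulates all grades and presents post-randomisation events by arm. Vorinostat nausea or fever therefore has a controlled route into the results outside the solicited table.

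Three further limits also stand. Protocol 1.1.1.C summarises the cancer setting and gives no onset time after a single dose. Comparison with the earlier study of both vaccines in HIV infection (Protocol 1.2.5.C) is unequal in any case, since that study recorded events for at least 7 days. The lack of a control diary follows from an open-label design without placebo, and no tabulation can supply one.

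What the reply does not remove is the overlap itself. The general promise to describe timing does not require solicited events to be set against the first vorinostat dose.

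**Conclusion.** The point holds in a narrow form. One or two of the three post-MVA diary days fall on or after the first vorinostat dose, and the SAP has no rule to separate solicited nausea or fever that begins then. This rests on the schedule being kept as written and on the participant starting vorinostat. Local reactions, the ChAd diary and all entries before the dose are not affected.

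The size cannot be derived from the documents. The range of roughly 1 to 5 of 30 participants depends wholly on assumed rates. The primary endpoint and the comparison of arms are untouched. This is a minor matter in a descriptive, single-arm secondary safety outcome, worth acting on because the remedy is cheap.

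**What to change.** In SAP 4.8:

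- State whether diary day 1 is the day of vaccination or the day after.
- Tabulate solicited events separately for ChAd and MVA.
- Split post-MVA general reactions by onset before or after the first vorinostat dose. A reaction that began earlier and persists stays in the first row; a later onset goes in a row labelled MVA plus vorinostat. Splitting by date of entry would wrongly move persisting MVA reactions into the second row.
- State in advance how an onset on the day of the dose is classified if the card gives no clock time.
- Keep participants who never start vorinostat wholly in the first row.
- Show ChAd for the matching diary days.

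The cost is a few lines of SAP text and one more table, from diary entries already made daily. The MVA-only window becomes shorter, at 1 or 2 diary days, and attribution within the overlap stays unresolved. No change to dosing or visits is involved.
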